## 9.0 STATISTICAL CONSIDERATIONS AND DATA MANAGEMENT

### 9.1 General Considerations

Data management and statistical analyses will be the responsibility of the study team. The randomization sequence, though, will be generated by a member of the Department of Biostatistics. Parameter estimates and relevant summary statistics will be reported for both efficacy and side effects. Continuous variables will be summarized by means, medians, minima, maxima, and standard deviations. Categorical variables will be summarized by frequencies and percentages. Additional exploratory analyses will be performed when appropriate. Normality of variables will be checked and, if violated, nonparametric methods will be adopted. Changes from the analysis plan will not require an amendment to the protocol unless it changes a significant feature of the study.

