### DESIGN

Our objectives will be met by performing two studies. The first is a 10-week, randomized, controlled, single-blinded, two-arm, parallel group, pilot trial at a single center and the second is a cross-sectional two-group comparative study.

Study I: A total of 40 persons with HIV may be screened and consented to identify the 32 participants to be enrolled and randomized into the pilot trial. We expect a screen failure rate of 20%. These participants will be  $\geq 18$  years old, have been receiving antiretroviral therapy with an HIV viral load  $< 75$  copies/mL within three months of the Entry Visit, and have an ISI score  $\geq 11$  within three months of the Entry Visit. These participants will be randomized 1:1 (stratified by age  $<40$  vs.  $\geq 40$  years) to either insomnia treatment with the SHUTi cognitive behavioral therapy program (N=16) or usual care (N=16).

Study II: The 32 participants with insomnia from Study I will then be compared to a similar group of 12 HIV-infected patients but with an ISI score  $< 11$  within three months of the Entry Visit. Six will be  $<40$  years old and the other six will be  $\geq 40$  years old). Approximately 15 persons with HIV may be screened and consented to identify this second group of 12 participants without insomnia. We expect a screen failure rate of 20%.

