#### 6.2.6.9 Fatigue, Resistance, Ambulation, Illnesses, & Loss of Weight (FRAIL) Scale

The FRAIL Scale is a screening test to assess frailty that predicts development of disability, decline in health functioning, and overall mortality (32). Frail scale scores range from 0–5 (i.e., 1 point for each component; 0=best to 5=worst) and represent frail (3–5), pre-frail (1–2), and robust (0) health status. The components and scoring of the FRAIL scale are as follows:

- Fatigue: “How much of the time during the past 4 weeks did you feel tired?” 1 = All of the time, 2 = Most of the time, 3 = Some of the time, 4 = A little of the time, 5 = None of the time. Responses of “1” or “2” are scored as 1 and all others as 0.
- Resistance: “By yourself and not using aids, do you have any difficulty walking up 10 steps without resting?” 1 = Yes, 0 = No.
- Ambulation: By yourself and not using aids, do you have any difficulty walking several hundred yards?” 1 = Yes, 0 = No.
- Illnesses: For 11 illnesses, participants are asked, “Did a doctor ever tell you that you have [illness]?” 1 = Yes, 0 = No. The total illnesses (0–11) are recoded as 0–4 = 0 and 5–11 = 1. The illnesses include hypertension, diabetes, cancer (other than a minor skin cancer), chronic lung disease, heart attack, congestive heart failure, angina, asthma, arthritis, stroke, and kidney disease.
- Loss of weight: “How much do you weigh with your clothes on but without shoes? [current weight]” “One year ago in (MO, YR), how much did you weigh without your shoes and with your clothes on? [weight 1 year ago]” Percent weight change is computed as:  $[(\text{weight 1 year ago} - \text{current weight}) / \text{weight 1 year ago}] * 100$ . Percent change > 5 (representing a 5% loss of weight) is scored as 1 and < 5 as 0.

The FRAIL scale will be assessed only at the Entry Visit.

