### 9.2 Sample Size Justification

As a pilot trial, no formal sample size estimation was performed as we do not expect to find significant differences in the comparisons to be performed for either Study I or Study II. The sample sizes of 32 participants (40 screened and consented to identify the 32) with insomnia for the Study I trial and the additional 12 (15 screened and consented to identify the 12) participants without insomnia for the comparison studies for Study II should be sufficient as per Julious (34). We expect a dropout rate of 25% for the RCT based on our ongoing study of depression CBT; thus, approximately 12 in each group will likely complete the proposed trial. It is unlikely that there will be sufficient power with just 12 per study arm for statistical hypothesis testing. However, we do not believe it necessary to find statistically significant differences between study arms at this stage as long as we can demonstrate that the SHUTi intervention can be implemented successfully by our group

and that the effect sizes related to differential outcomes in the two study arms are clinically relevant. Of note, the prevalence rate of ISI scores  $\geq 15$  in patients from the Eskenazi HIV clinics who would be eligible for the currently proposed pilot trial is 25%. Given that there are over 800 patients on stable HIV therapy in these clinics and our group’s proven ability to recruit in these clinics, we should have no difficulties enrolling 32 participants with insomnia into the Aim #1 trial.

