#### 9.10 Analysis Plan for the Primary Objective

To test our primary hypothesis, an analysis of covariance (ANCOVA) will be performed to test for treatment group differences in Week 10 ISI adjusted for baseline ISI using the intent-to-treat set. Statistical significance will be considered if two-sided p-value  $<0.05$ . This analysis will be also repeated using the per-protocol set.

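### The normality rule in section 9.1 tests variables rather than model residuals and does not exempt the primary ANCOVA, so it can displace a valid baseline-adjusted analysis after the data are seen (minor)

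*Combined protocol and SAP*

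**What the plan says.** Section 9.1 (General Considerations) sets a rule for all analyses: "Normality of variables will be checked and, if violated, nonparametric methods will be adopted". It gives no test, no cut-off and no named replacement. The same section promises parameter estimates and summary statistics, including means and SDs. It also allows changes from the analysis plan without an amendment unless a significant feature of the study changes.

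Section 9.10 (Analysis Plan for the Primary Objective) states that "an analysis of covariance (ANCOVA) will be performed to test for treatment group differences in Week 10 ISI adjusted for baseline ISI", in the intention-to-treat set and at a two-sided 5% level. It gives no fallback and does not say whether the rule in 9.1 applies to it.

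Section 9.2 (Sample Size Justification) declines to claim power. It says significance is not needed provided that the intervention can be implemented and that "the effect sizes related to differential outcomes in the two study arms are clinically relevant".

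Study I eligibility requires a screening ISI of at least 11 (sections 4.1.5 and 10.2.1). The ISI is completed again at the Entry Visit (section 3.4 and the schedule in 6.1). Section 9.10 does not say which score is the baseline.

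**The concern.** The normality assumption in ANCOVA concerns the residuals. The baseline is a covariate and may have any shape. The pooled Week 10 score combines two arms that the hypothesis says should differ. A check on the raw variables can therefore fail when the model is sound. A screening ISI cut off at 11 is an obvious candidate for failing it.

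If the check fails, 9.1 calls for a switch to a method that nobody has named, chosen with the data in hand. Three things follow:

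- The primary method is not fixed in advance.
- The baseline-adjusted mean difference with its confidence interval is no longer assured as the primary result. It is the most useful estimate for planning the next trial, and 9.2 judges the pilot partly on effect sizes.
- Section 9.14 plans multiple imputation, and the plan does not say how results from a rank method would be combined across imputed datasets.

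**Working it through.** **Inputs from the documents.** "These participants will be randomized 1:1", 16 per arm. "We expect a dropout rate of 25% for the RCT". Two-sided alpha 0.05.

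**The plan's own figure.** 16 × (1 − 0.25) = 12, which agrees with "approximately 12 in each group will likely complete the proposed trial". The plan gives no effect size, ISI SD or baseline-to-Week-10 correlation, so nothing else can be reproduced.

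**Assumed inputs.** Effect d = 0.8 or 1.0 in Week 10 SD units; correlation ρ = 0.3, 0.5 or 0.7; Week 10 SD 5; baseline ISI a rounded normal (mean 13, SD 6) truncated to 11–28; Shapiro-Wilk test at 0.05; 1,500 runs per setting (Monte Carlo error about ±2.5 points). The rule was modelled as a Mann-Whitney test on Week 10 ISI if baseline or Week 10 ISI fails the check, and ANCOVA otherwise.

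**Step 1: what baseline adjustment is worth.** Adjustment multiplies the outcome SD by √(1 − ρ²). At ρ = 0.5 this is √0.75 = 0.866, so the unadjusted interval is about 1/0.866 = 1.15 times as wide. At ρ = 0.3 the ratio is 1.05, and at ρ = 0.7 it is 1.40. By normal approximation, power = Φ(d/√(1 − ρ²) × √(n/2) − 1.96). With n = 12, d = 1 and ρ = 0.5:

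- adjusted: Φ(2.449/0.866 − 1.96) = Φ(0.87) = 81%
- unadjusted: Φ(2.449 − 1.96) = Φ(0.49) = 69%

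The approximation runs somewhat high at this sample size; the simulation below is the better guide.

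**Step 2: does the check look at the right thing?** With the truncated baseline and well-behaved model errors, Shapiro-Wilk rejected baseline ISI in about 42–45% of trials at 12 per arm and 60–64% at 16 per arm. It rejected the ANCOVA residuals in only about 4–6%. The rule then fires often when ANCOVA is valid.

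**Step 3: power at 12 per arm, truncated baseline.**

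| d | ρ | ANCOVA | Rank test, Week 10 | Rank test, change | Rank ANCOVA | Rule as modelled |
|---|---|---|---|---|---|---|
| 0.8 | 0.3 | 48% | 42% | 39% | 46% | 45% |
| 0.8 | 0.5 | 54% | 42% | 50% | 50% | 48% |
| 0.8 | 0.7 | 71% | 39% | 69% | 64% | 56% |
| 1.0 | 0.3 | 66% | 60% | 55% | 64% | 62% |
| 1.0 | 0.5 | 75% | 59% | 69% | 71% | 67% |
| 1.0 | 0.7 | 89% | 59% | 88% | 85% | 74% |

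From the unrounded figures at ρ = 0.5, the rule costs 53.8 − 47.7 = 6.1 points at d = 0.8 and 74.5 − 66.7 = 7.8 points at d = 1.0. A switch in every trial would cost 74.5 − 59.3 = 15.2 points at d = 1.0. A second simulation that takes the truncated screening ISI as the baseline gives an average loss of about 12 points at d = 1.0, ρ = 0.5. If the average loss is roughly the trigger rate times the 15.2-point gap, 12 points needs the check to fail in about 12/15.2 = 79% of trials, so that figure is the upper end. Rank ANCOVA loses about 1–7 points across the table.

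**Step 4: if the baseline is the re-measured Entry ISI.** Assumed: clinic SD 6 calibrated to the 25% with ISI of at least 15 in section 9.2, retest correlation 0.6–0.8, d = 1.0, 12 per arm, 3,000 runs. The check failed in 9–12% of trials. That is close to 1 − 0.95² = 9.75%, the rate expected when two independent, normal variables are each tested at 5%. Power at ρ = 0.5 fell from about 74% to 72%. Over ρ = 0.3–0.7 the loss was 0.5–3.6 points.

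**Step 5: type I error.** It stayed at about 4–6%. The rule does not inflate false positives in these settings.

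**The case against.** The case on the other side is substantial.

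- **Section 9.10 may govern.** It names ANCOVA without condition, and a specific clause can be read as overriding a general one. That is a fair reading, but the text does not say so, and one sentence would settle it.
- **The truncated score may not be the baseline.** The cut at 11 applies at screening, and nothing requires the Entry ISI to meet it again. If the Entry score is the covariate, the average loss is about 2 points. This stands, and it is why the size must be given as a range.
- **The replacement is unknown.** The primary objective speaks of 10-week changes, so a rank test on change is a natural candidate. At ρ = 0.7 it comes close to ANCOVA (69% against 71% at d = 0.8), although it loses 9 points at ρ = 0.3. A rank ANCOVA loses little anywhere. This also stands, but a plan that leaves the choice open does not exclude the worst option.
- **Power is a weak ground.** Section 9.2 disclaims it. Agreed: the case rests mainly on fixing the method and the estimate in advance.

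Two stronger readings are tempting, and the documents support neither. A reader might infer that the effect size is lost altogether. Section 9.1 promises parameter estimates, means and SDs, so an unadjusted difference survives. A reader might also infer that the rule strips an age adjustment from the Study II frailty comparisons, because a FRAIL score built as "1 point for each component; 0=best to 5=worst" will hardly look normal. Sections 9.10 and 9.11 cover only SHUTi against usual care, so no age-adjusted Study II analysis is planned that could be displaced. A rank comparison of such scores is also defensible.

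**Conclusion.** The point holds as a minor one. Section 9.1 aims the check at variables instead of residuals, names no replacement, and leaves open whether it applies to the primary ANCOVA. Read literally, it can displace a valid primary analysis after the data are seen, and the adjusted mean difference with its interval is then not guaranteed as the primary result.

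At 12 per arm, d = 1 and ρ = 0.5, the gap between ANCOVA and an unadjusted rank test is about 75% against 59%. It would be wrong to take that 16-point gap as the expected cost, because it assumes the switch always happens and always goes to an unadjusted test. Averaged over the rule, the loss is about 6–12 points with a truncated baseline and about 2 points with a re-measured one. If a rank ANCOVA is the replacement, even a certain switch costs only about 4 points here. All of these rest on assumed effect sizes, correlations and score distributions, because the plan gives none. Heavy-tailed residuals were not simulated and could favour a rank method.

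**What to change.** In sections 9.1 and 9.10, state that:

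- the ANCOVA of Week 10 ISI adjusted for baseline ISI remains the primary analysis whatever the normality checks show;
- only the model residuals are inspected;
- the adjusted mean difference is reported with its 95% CI;
- one named method (a permutation p-value, a bootstrap interval or a rank ANCOVA) is run as a sensitivity analysis.

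It would help to say in the same place which ISI score, screening or Entry, is the baseline.

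The cost is SAP wording and slightly more analysis work, with no change to visits or data collection. The downside is a possible small loss of power if the residuals prove truly heavy-tailed; the sensitivity analysis would help to show that.

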### 9.2 Sample Size Justification

As a pilot trial, no formal sample size estimation was performed as we do not expect to find significant differences in the comparisons to be performed for either Study I or Study II. The sample sizes of 32 participants (40 screened and consented to identify the 32) with insomnia for the Study I trial and the additional 12 (15 screened and consented to identify the 12) participants without insomnia for the comparison studies for Study II should be sufficient as per Julious (34). We expect a dropout rate of 25% for the RCT based on our ongoing study of depression CBT; thus, approximately 12 in each group will likely complete the proposed trial. It is unlikely that there will be sufficient power with just 12 per study arm for statistical hypothesis testing. However, we do not believe it necessary to find statistically significant differences between study arms at this stage as long as we can demonstrate that the SHUTi intervention can be implemented successfully by our group

and that the effect sizes related to differential outcomes in the two study arms are clinically relevant. Of note, the prevalence rate of ISI scores  $\geq 15$  in patients from the Eskenazi HIV clinics who would be eligible for the currently proposed pilot trial is 25%. Given that there are over 800 patients on stable HIV therapy in these clinics and our group’s proven ability to recruit in these clinics, we should have no difficulties enrolling 32 participants with insomnia into the Aim #1 trial.

#### 9.4 Criteria for Stopping the Study

No early stopping rule will be implemented.

#### 9.5 Analysis Datasets

Datasets	Definition
Intention-to-treat (ITT)	This will comprise all patients who meet the eligibility criteria and are randomized onto the study irrespective of their compliance to the planned course of treatment.
Per Protocol Set	This will comprise all UC patients and SHUTi participants.
Safety	This will comprise the SHUTi patients that attend at least one session of treatment.

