### 3.3 Study I Randomization

For those patients eligible for the pilot trial in Study I, they will be randomized at their Entry Visit. Randomization will be stratified by age (<40 years and  $\geq 40$  years). The randomization sequence will be placed in opaque envelopes that will only be opened and witnessed at the Entry Visit.

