### 4.2 Exclusion Criteria

- 4.2.1 Inability to complete written, informed consent.
- 4.2.2 Incarceration at the time of any study visit.
- 4.2.3 Active suicidality, as determined by the patient's HIV provider or social worker following a positive response (1, 2, or 3) to PHQ-9 Item #9 and a positive response (yes) to one or more of the three questions (for Question #3, the previous attempt must be within the past 10 years) on the Patient Suicidality Form (see Appendix).
- 4.2.4 Diagnosed vascular disease (documented history of angina pectoris, coronary disease, peripheral vascular disease, cerebrovascular disease, aortic aneurysm, or otherwise known atherosclerotic disease).
- 4.2.5 History of congestive heart failure, even if currently compensated.
- 4.2.6 Diagnosed disease or process, besides HIV infection, associated with increased systemic inflammation (including, but not limited to, systemic lupus erythematosus, inflammatory bowel diseases, other collagen vascular diseases).

Note: Hepatitis B or C co-infections are NOT exclusionary

- 4.2.7 Known or suspected malignancy requiring systemic treatment within 180 days of the Entry Visit.

NOTE: Localized treatment for skin cancers is not exclusionary.

- 4.2.8 Therapy for serious medical illnesses within 14 days prior to screening.

Note: Therapy for serious medical illnesses that overlaps with a main study visit will result in postponement of that study visit until the course of therapy is completed; postponement outside of the allowed study visit timeframe will result in study discontinuation.

- 4.2.9 Pregnancy or breastfeeding during the course of the study.

- 4.2.10 Receipt of investigational agents, cytotoxic chemotherapy, systemic glucocorticoids (of any dose), or anabolic steroids at the Entry Visit.

Note: Physiologic testosterone replacement therapy or topical steroids is not exclusionary. Inhaled/nasal steroids are not exclusionary as long as the participant is not also receiving HIV protease inhibitors.

- 4.2.11 Active drug use or dependence that, in the opinion of the investigator, would interfere with adherence to study requirements.

- 4.2.12 History of schizophrenia, bipolar disorder, or dementia.

NOTE: Depression is not exclusionary as long as the severity of depression does not impede ability to perform the required study procedures.

- 4.2.13 Musculoskeletal or neurologic disorders that impede ability to perform the required study procedures.

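### Membership of the ITT set for the primary analysis depends on eligibility, and nothing limits that judgement to facts known before randomisation

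*Combined protocol and SAP*

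**What the plan says.** Section 9.5 defines the ITT set as follows: "This will comprise all patients who meet the eligibility criteria and are randomized onto the study". Two conditions must both hold, eligibility and randomisation. The only thing expressly set aside is compliance.

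Section 9.10 tests "treatment group differences in Week 10 ISI adjusted for baseline ISI using the intent-to-treat set", two-sided at 0.05, so this definition fixes who enters the primary analysis.

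Section 3.3 gives the timing: eligible patients are chosen and "they will be randomized at their Entry Visit". Section 3.5 places the Week 10 Visit 63 to 84 days later.

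Two exclusion criteria in Section 4.2 are worded to run past that point: 4.2.2, "Incarceration at the time of any study visit", and 4.2.9, "Pregnancy or breastfeeding during the course of the study".

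Section 8.0 also lists pregnancy or breastfeeding arising during the study as a reason for discontinuation. It does not say whether that participant stays in the ITT set. Section 9.14 provides multiple imputation for missing data, with sensitivity analyses if missingness differs.

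**The concern.** An ITT set protects the comparison because its membership is fixed at randomisation. Here membership also depends on a condition that, for two criteria, can change afterwards, and the text does not fix the date at which it is judged. A participant who is incarcerated at Week 10, or who becomes pregnant, could be said no longer to satisfy Section 4. So could a participant in whom a baseline ineligibility comes to light after allocation.

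Removal on such grounds need not be balanced between arms. SHUTi participants have up to six sessions arranged with study staff (Section 3.4.1), while Usual Care has no formal contact between the two visits (Section 3.4.2). The schedule in Section 6.1 lists no pregnancy test, so later events could be noticed more readily in one arm.

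Section 9.2 makes the size of the difference between arms a main product of this pilot, so it matters who is in the set even though the trial is not powered for a test.

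**Working it through.** **Inputs.** 32 randomised 1:1, 16 per arm (Section 3.1); 25% dropout expected, leaving about 12 per arm (Section 9.2); about 25% women (Section 10.7); randomisation at the Entry Visit (3.3); Week 10 Visit at day 63 to 84 (3.5). The documents give no rate for later 4.2.2 or 4.2.9 events and no SD for ISI.

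**The plan's own figure.** 16 × (1 − 0.25) = 12 per arm. This reproduces and is not in dispute.

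**Timing of the criteria.** Several exclusions are tied to a date: 4.2.7 to 180 days around entry, 4.2.8 to 14 days before screening, 4.2.10 to the Entry Visit itself. Criteria 4.2.2 and 4.2.9 are not:

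| Criterion | Can be met at entry (day 0)? | Can first be met after randomisation? |
|---|---|---|
| 4.2.2 incarceration | Yes | Yes, at the Week 10 Visit, day 63 to 84 |
| 4.2.9 pregnancy or breastfeeding | Yes | Yes, at any time up to the end of follow-up |

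**Combining the sections.** Membership under 9.5 is randomised AND eligible. The protective clause covers compliance, and neither event is non-compliance with the course of treatment. No section says that eligibility is judged at entry only, and none says that a participant with a later event is kept. Section 9.14 can act only on people who are in the set. By contrast, the per-protocol set in 9.5 carries no eligibility condition, so read literally it could be larger than the ITT set.

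**Size per removal.** 1/16 = 6.25% of an arm and 1/32 = 3.1% of the trial. If k are removed, the set is 32 − k.

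**How often.** The per-participant probability p is an assumption, shown only as a range. Expected removals are 32p; the chance of at least one is 1 − (1 − p)^32.

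| p (assumed) | Expected removals | Chance of at least one |
|---|---|---|
| 1% | 0.3 | 28% |
| 3% | 1.0 | 62% |
| 5% | 1.6 | 81% |
| 10% | 3.2 | 97% |

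Applying one p to all 32 is generous for 4.2.9, since only about 32 × 0.25 = 8 women are expected.

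**Effect on the estimate, case 1: Week 10 ISI observed.** Assume complete outcomes, equal SDs, and k removals from one arm. The standard error of the unadjusted difference grows by √(1/16 + 1/(16 − k)) / √(2/16): 1.017 for k = 1 and 1.080 for k = 4. If those removed lie d from the full-arm mean, the mean of those left moves by d × k/(16 − k). With d = 1 SD (assumed), that is 1/15 = 0.067 SD for k = 1 and 4/12 = 0.33 SD for k = 4.

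**Case 2: Week 10 ISI not observed.** There is no score to remove, so the choice is between imputing and omitting. If the imputation used only arm and baseline ISI, the ANCOVA estimate would be nearly the same either way. A difference arises through other variables in the imputation model, through the sensitivity analyses in 9.14, and through the reported denominator. Some of these people may already be among the 16 − 12 = 4 per arm expected to drop out.

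**The case against.** The best defence is that eligibility comes before randomisation in this protocol. Section 3.3 randomises patients already found eligible, and Section 4.0 is headed as selection and enrolment criteria. In that order, the phrase in 9.5 most naturally means eligible at entry. Section 8.0 answers a later pregnancy with discontinuation, and the end of Section 4.2 allows an excluded person's visit to be rescheduled. Nowhere is such a person said to leave the analysis. The trial is also a pilot that does not expect significant differences.

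Much of this stands. Both criteria do cover status at entry, the entry-only reading is plausible, and removal is a literal reading rather than a stated rule. What remains is that 9.5 does not state the entry-only reading and no other section supplies it.

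Three stronger inferences are tempting and are not supported:

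- A reader might infer that one removal shifts an arm mean by about half an ISI point (an assumed 8-point deviation over 16). That needs an observed Week 10 ISI, which a participant discontinued or still incarcerated would usually lack.
- A reader might infer that the conflicting entry windows make some randomised patients ineligible. The 60-day figure is in the Entry Visit procedures (Section 3.4). Criterion 4.1.4 gives 90 days for viral load and 4.1.5 gives no ISI window, so entry at day 61 to 90 still satisfies Section 4. That conflict is a separate inconsistency.
- A reader might infer that the plan provides for unblinded re-judgement of eligibility. No review of eligibility after randomisation is described; the wording merely leaves room for one.

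**Conclusion.** The point holds as a defect of definition. Read literally, Section 9.5 permits a randomised participant to be left out of the primary ANCOVA because of an event after randomisation, or because of ineligibility discovered later. The documents neither exclude that reading nor direct it.

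The likely size is small. Each removal costs 6.25% of an arm. The number of removals is unknown, and the 1% to 10% range above is an assumption. The shifts in case 1 apply only where a Week 10 ISI exists, most plausibly when a baseline ineligibility is found late. For most later events, case 2 applies. The point does not show that the primary result would be biased. It is worth correcting because the arms are small, the effect estimate is a stated aim, and the correction costs almost nothing.

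**What to change.** - In Section 9.5, define the ITT set as all randomised Study I participants, analysed in the arm assigned, and delete the eligibility condition.
- State that a participant with a later 4.2.2 or 4.2.9 event stays in the set, and that Section 9.14 applies if the Week 10 ISI is missing.
- Optionally, add a sensitivity analysis that omits participants ineligible on facts known before randomisation.
- Reconcile Sections 4.2.9 and 8.0 on whether a pregnancy arising after entry is an eligibility criterion or a discontinuation reason. This review takes no view on the clinical rule.

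The cost is one sentence of definition and a cross-reference. No new data, visits or participants are needed.

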### 3.4.2 Usual Care

Patients randomized to the Usual Care group will be encouraged to follow-up with their primary care or HIV provider. There will be no formal interaction with the participants between the Entry Visit and the Week 10 Visit. However, the participants will be encouraged to contact the study team for any changes in their condition. There will be no restrictions on the care that can be received, although we will assess changes in care during the trial.

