If an enrolled participant reports having thoughts of being better off dead or of hurting him/herself during any telephone calls (e.g., a scheduling call or a call to the study team initiated by the participant), the exact same procedures as outlined above will immediately be initiated. Please see the Appendix for the full Suicide Management Plan.

Since it is unknown if depression therapy (or lack thereof) results in somatic adverse events in antiretroviral-treated HIV-infected patients, we will also carefully document Grade 3 or 4 level toxicities defined using the Division of AIDS Table for Grading Adult Adverse Experiences. Clinical management decisions and decisions to discontinue participants from the trial will be made by the principal investigator(s) in conjunction with the participant's primary caregiver; care plans and outcomes must be included in the source documentation.

All serious adverse events (SAEs) will be documented on CRFs with unexpected SAEs forwarded to the IUPUI IRB within 10 working days of the event and the remainder to be documented on the annual continuing review.

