#### 9.11 Analysis Plan for Secondary Objectives

Both unadjusted comparisons and adjusted comparisons between UC and SHUTi will be performed for secondary outcomes. Safety assessments will be performed using the safety dataset.

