#### 10.6 Data and Safety Monitoring Plan

- Progress of these studies, including data monitoring, participant enrollment, protocol deviations, and all SAE, will be reviewed by a panel including the PIs (Drs. [name] and [name]) and an HIV expert investigator at Indiana University not directly connected with this study ([name] of the Division of Infectious Diseases, Indiana University School of Medicine). Reports, which will include descriptions of all adverse events, will be prepared for review by this panel every 12 months. Any study participant prematurely discontinued due to an adverse event will be reviewed immediately. Standard procedures for reporting deviations from protocols to the Indiana University ICRC, IRB, and NHLBI will be implemented. Serious Adverse Events (SAEs) will also be reported to the IRB within 30 working days and subsequently forwarded to NHLBI as required.

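### The planned adverse-event analysis covers SHUTi attenders only, so it has no concurrent Usual Care comparator, although events are documented without restriction by arm

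*Combined protocol and SAP*

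**What the plan says.** The table in 9.5 defines the safety dataset: "This will comprise the SHUTi patients that attend at least one session of treatment". Section 9.11 then states: "Safety assessments will be performed using the safety dataset". No other safety population is defined.

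Section 7.0 gives the reason for recording events and its scope. The reason is: "Since it is unknown if depression therapy (or lack thereof) results in somatic adverse events in antiretroviral-treated HIV-infected patients". The scope is that "we will also carefully document Grade 3 or 4 level toxicities defined using the Division of AIDS Table for Grading Adult Adverse Experiences", and "All serious adverse events (SAEs) will be documented on CRFs". Neither statement is limited to one arm.

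Three other places touch on safety reporting:

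- Section 9.1: "Parameter estimates and relevant summary statistics will be reported for both efficacy and side effects". It names no population and no comparison by arm.
- Section 10.3.2.4 has all adverse events graded.
- Section 10.6: "Reports, which will include descriptions of all adverse events, will be prepared for review by this panel every 12 months". This is oversight, and no comparison by arm is specified.

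Contact between visits differs by arm. Section 3.4.1 provides up to six SHUTi sessions, each with staff contact in person or by telephone. For Usual Care, 3.4.2 says: "There will be no formal interaction with the participants between the Entry Visit and the Week 10 Visit".

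**The concern.** Section 7.0 justifies documenting events by uncertainty about therapy and about its absence. The second half of that can be informed only by people who do not receive the therapy, and those are the people whom 9.5 leaves out.

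Followed as written, the trial would report an event count in up to 16 SHUTi attenders with nothing concurrent beside it. Events unrelated to SHUTi could be read as harm, or a real excess could be put down to background. Section 2.2 says that SHUTi has not been tested specifically in people with HIV, and the reassurance in 10.4 comes from HIV-uninfected users. The Usual Care arm is therefore the only reference group inside the trial.

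**Working it through.** **Inputs from the documents.** 32 randomised 1:1, 16 per arm (3.1); 25% dropout and about 12 completers per arm (9.2); the safety set as in 9.5. The documents give no adverse-event rate, so every rate below is an assumption, shown over a range.

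**The plan's own figure.** 16 × (1 − 0.25) = 12 completers per arm, as 9.2 states.

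**Who is in the safety set.** Usual Care: 0 of 16. SHUTi: at most 16. Outside the set: at least 16/32 = 50% of those randomised, plus any SHUTi participant who attends no session.

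**What a one-arm count can show** (exact two-sided 95% limits, n = 16):

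- 0 events: upper limit 1 − 0.025^(1/16) = 20.6%.
- 1 event: 1/16 = 6.3%, interval 0.2% to 30.2%.

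**Chance of at least one event in 16 SHUTi participants if SHUTi has no effect**, 1 − (1 − p)^16:

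| Assumed 10-week rate p | Chance of at least one event |
|---|---|
| 5% | 56% |
| 10% | 81% |
| 20% | 97% |

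At such rates a SHUTi-only table would probably contain events that it cannot attribute. At much lower rates it would probably be empty.

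**What adding Usual Care buys.** The set grows to as many as 32, and a difference between arms can be estimated. With the same assumed rate in both arms, the approximate 95% half-width is 1.96 × √(2p(1 − p)/16):

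| Assumed rate p | Half-width, percentage points |
|---|---|
| 5% | 15.1 |
| 10% | 20.8 |
| 20% | 27.7 |
| 30% | 31.8 |

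The normal approximation is rough here, since 5% of 16 is only 0.8 expected events per arm. For a true contrast of 10% against 30%, two-sided power at 0.05 is about 17% with Fisher's exact test (29% by the normal approximation). The comparison can only be descriptive.

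**Ascertainment.** SHUTi participants have up to six contacts at which an event may surface, and Usual Care has none that are scheduled. With equal true rates, more events would tend to be found under SHUTi. Merging the arms into one table without showing how events were found would bring in that bias.

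**Data available at Week 10.** The schedule in 6.1 collects updated diagnoses, updated medications and the PHQ-9 in both arms, but it has no row for eliciting adverse events. A comparison restricted to Week 10 would also miss people who leave earlier, for whom 9.2 expects 25%.

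**The case against.** The strongest reply is that this is a small pilot of an online programme. Section 10.2.3 rates the risks as minimal and names no known SHUTi risk, 9.2 disclaims power for hypothesis testing, and safety is not among the objectives in section 1.0. Usual Care events are still documented under 7.0, graded under 10.3.2.4 and described to the panel under 10.6. PHQ-9 change is a secondary outcome compared between arms (1.2.2, 9.11), so overall depressive worsening already has a concurrent comparator. All of this stands, and it limits the weight of the point. It does not supply an adverse-event table by arm, which no section provides.

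Three stronger readings are tempting, and the documents do not support them:

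- A reader might infer that Usual Care safety data are lost. They are not; the gap is in the analysis set.
- A reader might infer that the trial set itself a comparative safety question. The clause in 7.0 is a reason for documenting events, and it speaks of depression therapy, whereas this trial treats insomnia and does not require depression for entry.
- A reader might infer that background events are known to be common. No rate is given. Section 7.0 says only that participants may have depression, 4.2 excludes several serious conditions and active suicidality, and the Suicide Management Plan expects positive screens for ideation to be rare, with none among enrolled participants in two earlier depression trials.

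**Conclusion.** The point holds as a gap in the analysis plan. Under 9.5 and 9.11 the adverse-event analysis has no concurrent comparator: 0 of 16 Usual Care participants are in it, and at least half of those randomised are outside it. This sits badly with 7.0, which documents events regardless of arm and invokes the absence of therapy as part of its reason. The membership counts follow from the text alone; the probabilities, half-widths and power rest on assumed event rates.

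A reader might also infer that adding Usual Care would let the trial separate a SHUTi effect from the natural course. At 16 per arm and with unequal contact it would not. It would put a concurrent count beside the SHUTi count, with wide uncertainty. The primary ISI analysis and the efficacy comparisons are unaffected. The change is worth making, but its practical weight in this pilot is modest.

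**What to change.** 1. In 9.5, define the safety set as all randomised participants.
2. In 9.11, tabulate Grade 3-4 events, SAEs and positive PHQ-9 item 9 descriptively by randomised arm, with a supplementary table by treatment received (at least one SHUTi session against none).
3. Include events in participants who drop out before Week 10.
4. Flag how each event was ascertained. Show separately the events found at the Week 10 visit in both arms and those found only at SHUTi contacts. State how Grade 3-4 events are elicited at Week 10, since 6.1 has no row for this.
5. Reconcile the depression-therapy wording in 7.0 with the insomnia intervention.

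The cost is one row in 9.5, a few sentences in 9.11 and 7.0, and an additional table or two with wide intervals. Event documentation is already planned without restriction by arm. The ascertainment flag, and any Week 10 elicitation question that is added, would be small additions to the CRF.
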